Paraprofessionals: 18 HV programs will receive the MB intervention delivered by paraprofessional home visitors. We will train ~72 home visitors from the 18 HV programs in this study arm, or ~4 home visitors per program; HV programs participating in this study currently employ between 3-8 home visitors, with most employing 4-5. All of the HVs will currently be a staff member of one of the participating study sites.

Home Visiting Supervisors/Managers/Directors: We will also be consenting approximately 15 home visiting supervisors/managers/directors from HV programs outside of the state of IL, to participate in a 5-10 minute survey about their experiences with the Mothers and Babies Program from their perspective as a home visiting program manager/director. The survey responses will help guide improvements and innovations as we continue to support the integration of Mothers and Babies into home visiting!

4.0 Procedures Involved:

Program Implementation: This project is a cluster randomized trial to be conducted in 42 HV programs across Illinois and adjacent states. Cluster allocation by HV program minimizes contamination between study groups that would likely occur if randomization were conducted at the home visitor level. Recruitment of women from throughout Illinois and adjacent states will allow us to increase study generalizability by enrolling a more geographically and demographically diverse sample than could be obtained by working in solely one part of the state. We will randomize 18 HV programs to implement MB with mental health professionals, 18 HV programs to implement MB with paraprofessional home visitors, and 6 HV programs to implement usual home visiting services.

Each HV program delivering MB (both the clinician- and home visitor-led arms), will implement five MB groups/cohorts. Each cohort will have approximately 8 women, which will allow us to reach our target of 40 study participants per program. This cohort size is consistent with previous MB trials. One

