The plan for supervision was carefully developed to ensure a sufficient level of supervision while not placing undue time commitments on home visitors and clinicians implementing MB. Initially, supervision for home visitors and mental health professionals will be conducted via one hour weekly Skype sessions with [name]. During these sessions, [name] will first debrief the completed MB session and will then help the home visitors and mental health professionals plan for the subsequent group session. Accordingly, our Intervention Coordinator will schedule Skype sessions that consist of 2-3 individuals who are implementing on the same schedule. This will allow home visitors and clinicians to benefit from both [name] supervision and the perspectives of colleagues implementing MB at the same time. Following the initial supervision, group facilitators will complete a brief survey after the completion of each cohort they facilitate, in order to reflect on the frequency and types of supervision utilized during a specific cohort.

Program Intervention: Study participants will be randomly selected to participate in one of three study arms; Groups led by paraprofessional home-visiting staff, groups led by Mental Health Consultants, or a control group. Women who participate in the group sessions will attend a two hour session, once a week, for six weeks at their home-visiting program site. The group facilitators will administer a short survey at the end of each group session, to obtain the study participant's feedback on the group session. Each group facilitator will be trained on the Mothers and Babies curriculum prior to beginning group implementation.

The Mothers and Babies Group Curriculum has been used in home visiting (HV) programs and has demonstrated positive outcomes for women who receive MB. The curriculum is comprised of 6 sessions. Mothers and Babies is divided into three overall sections, one on each of the following Cognitive Behavioral Theory components; Pleasant Activities, Thoughts, and Contact with Others. In each of these sections, participants are first taught to understand how the component influences her mood. This teaching of the relationships between CBT components and mood is referred to as

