Please note that communication with study participants will be based on participant preference and can be administered by phone, email, or text communication channels. We anticipate that it will take about 10-15 minutes for item #1 above. For items 2-5, we anticipate that these outreach efforts will take less than five minutes per participant, with many of our study participants being contacted for item #4 via text message.

Completed intervention sessions: Will be collected by mental health professionals and home visitors delivering MB on an attendance form created for use in this study. Fidelity of intervention implementation will be assessed by reviewing a random sample of audiotaped sessions. [name], research staff, and the Project Coordinator will perform independent ratings using fidelity checklists developed and used in previous trials by the PI to assess fidelity to MB. Retraining will be triggered for adherence <90%.

Acceptability: We will collect data on MB acceptability via three data collection activities. First, we will conduct brief semi-structured interviews with 90 intervention participants—45 who received MB led by mental health professionals and 45 who received MB led by paraprofessional home visitors. To ensure representativeness of this sample, the 45 participants per group will be stratified across the three regions of Illinois—Chicago, downstate Illinois, and adjacent states. Second, we will conduct brief semi-structured interviews with 24 home visitors who delivered MB. Again, we will divide respondents equally across the three regions (n=8 home visitors from Chicago, downstate Illinois, adjacent states, respectively). We will also conduct semi-structured interviews with all ~18 mental health professionals delivering MB. Third, all participants will complete brief paper and pencil checklists immediately after receiving a MB session. Home visitors and mental health professionals will collect these checklists. We will ask each intervention participant to rate each session using three questions used in previous MB studies: “how much did you enjoy today’s group session?”, “how well did you understand what we talked about during today’s group session?”, and “how often do you think you will use the skills and information that you were given during today’s group session?”

5.0 Multiple sites:

N/A

6.0 Incomplete Disclosure or Deception:

N/A

7.0 Recruitment:

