Home Visitors: We will recruit 72 home visitors from 42 participating HV programs throughout the state of Illinois and adjacent states. All HV programs recruit women at high risk for poor pregnancy and/or parenting outcomes via referrals from prenatal care clinics, community outreach, and current program participation. We will be training all of the 72 home-visitors who are being recruited through the participating home-visiting sites. Out of those 72 home-visitors, we anticipate 24 of them to implement the intervention groups and in turn be our study participants being asked to complete a semi-structured interview after the completion of their cohorts.

Study Participants: We will recruit 40 study participants from each of the 42 participating HV programs. These 40 participants per program will be recruited in five cohorts. Each cohort will be recruited for approximately one month at a participating HV program; as such, each month we recruit at a participating HV program we will only need to enroll 8 study participants (40 participants/5 cohorts).

Clinicians: We will also recruit and train ~18 clinicians to deliver MB; each clinician will deliver MB at one or more HV programs across the duration of the project. All of the clinicians who are implementing the intervention will be invited to participate in the semi-structured interviews after the completion of their cohorts. The 18 clinicians will live and work in the three different regions of Illinois where this study will be conducted: Chicago, downstate Illinois, and western Illinois, as well as adjacent states. A description of the study as well as the clinician role was sent out to the Illinois Association for Infant Mental Health (ILAIMH) listserv and the consultant email list at Illinois Children's Mental Health Partnership (ICMHP). [name], MS, the Consultation Coordinator at the Illinois Children's Mental Health Partnership (ICMHP) and coordinator of the Infant Mental Health Consultant network in Illinois, has identified clinicians from the three regions of the Illinois where this study will be conducted. We have also sent a description of the study to the Home Visiting Research Network (HVRN) to recruit adjacent states participation for wave 2 of recruitment.

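### Facilitators collect the session ratings for groups they led, with no shielding described, so the checklist part of the Aim 4 acceptability data may be inflated in both MB arms

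*Protocol*

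**What the plan says.** Protocol section 4.0 describes the end-of-session feedback twice. Under Program Intervention: "The group facilitators will administer a short survey at the end of each group session". Under Acceptability: "all participants will complete brief paper and pencil checklists immediately after receiving a MB session", and then "Home visitors and mental health professionals will collect these checklists". The protocol does not say outright that the survey and the checklist are one instrument, but they read that way.

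The content is short: "We will ask each intervention participant to rate each session using three questions used in previous MB studies". The three questions cover enjoyment of the session, understanding of what was discussed and expected use of the skills. No item names the facilitator.

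On who the facilitators are, section 3.0 (Paraprofessionals) says "All of the HVs will currently be a staff member of one of the participating study sites". Section 7.0 (Clinicians) describes clinicians recruited through professional lists and a consultant network, and says that "each clinician will deliver MB at one or more HV programs across the duration of the project". They are not described as program staff. In both MB arms the groups meet "once a week, for six weeks at their home-visiting program site".

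Section 14.0 requires instruments to carry only a study ID. Nothing in section 4.0 or 14.0 keeps a completed checklist from the eyes of the facilitator who collects it.

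**The concern.** A woman who hands a rating to the person who has just run her group has a reason to be kind. A study ID protects her identity in the database. It does not hide the answers from someone who takes the form from her hand in a group of about eight.

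The protocol recognises that women may worry about their standing with the program. Sections 9.0 and 14.0 assure them that declining to answer will not affect that relationship. The assurance covers refusal to answer. It does not cover giving a low rating.

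At stake is how the ratings are read. Of the three acceptability sources, the checklist is the only one that asks every woman in an MB group. If scores are high in both arms partly because of how they were collected, they could be presented as showing that the course is well accepted under either type of leader. Such ratings do get used: section 3.0 (Vulnerable Populations) cites favourable acceptability ratings from earlier use of the course.

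**Working it through.** The documents give no rating scale, expected mean, standard deviation or sample size for the checklist, so there is no planned figure to reproduce. The check is a reading of the passages, a count of exposed forms and a short argument about what can cancel.

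**1. Who handles the data, by source**

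| Source | Reaches | Handled by |
|---|---|---|
| Session checklist (4.0, Acceptability) | all women in MB groups | the facilitators |
| Participant interviews (4.0; 8.0) | 90 women, 45 per MB arm | research staff, by phone |
| Facilitator interviews (4.0; 8.0) | 24 home visitors, about 18 clinicians | research staff |
| Outcome surveys, including QIDS-SR16 (4.0) | all participants | REDCap or research-team contact |
| Fidelity (4.0) | random sample of recorded sessions | raters on the research side, from recordings |

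Among the participant-reported measures described, the checklist is the one that passes through the facilitator.

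**2. Number of exposed forms**

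- Intervention sites that ran at least one cohort: 29, made up of 15 clinician-led (MH) and 14 home visitor-led (HV) (SAP, Randomization Methods).
- Planned average recruitment: 27 women per site (SAP, Power and Sample Size Considerations).
- Sessions per woman: 6.
- Ceiling: 29 × 27 × 6 = 4,698 forms. By arm, this is 15 × 27 × 6 = 2,430 (MH) and 14 × 27 × 6 = 2,268 (HV).

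This assumes that the planned average held at these sites and that every woman attended all six sessions. It counts forms and does not measure bias. On the same inputs there are 29 × 27 = 783 women, so the 90 interviews would reach 90 / 783 = 11.5% of them.

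**3. How close is the HV-arm facilitator to the woman?**

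The plan trains about 72 home visitors at 18 programs, and "we anticipate 24 of them to implement the intervention groups". That is 24 / 72 = 33% of those trained, or 24 / 18 = 1.3 per program. If caseloads are equal and all of a program's home visitors are trained (both assumptions), about one woman in three would hand her form to her own home visitor. The others would hand it to a different staff member of her program.

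**4. What cancels and what does not**

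Write the observed mean rating in an arm as the true mean plus an inflation b.

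- Within an arm, the level is overstated by b, and nothing cancels.
- Between arms, observed difference (HV minus MH) = true difference + (b_HV − b_MH). If the two inflations are equal, they drop out.
- If inflation pushes scores to the top of the scale, a true difference shrinks even when the inflations are equal, and the arms look more alike than they are.

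The staff relationship is a plausible reason for b_HV to exceed b_MH. Nothing in the documents gives a value for either term or shows that they differ.

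**The case against.** A reader might infer that the HV versus MH acceptability comparison is biased in favour of home visitors. The documents do not support that, for four reasons.

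- **Same procedure in both arms.** Clinicians also collect ratings of their own sessions, and both arms meet at the woman's program site. Only a difference in inflation would bias a contrast, and none is shown. Clinicians came partly through a consultant network, and the documents do not say whether they had prior ties to the programs. Most women in the HV-led arm would probably not be handing the form to their own home visitor.
- **The items rate the session.** None asks about the facilitator. This softens the concern without removing it, because enjoyment and understanding are in part judgements on how the session was delivered.
- **There is an independent source.** Research staff run the 90 participant interviews by phone, equally divided between the MB arms. The concern does not reach them.
- **No between-arm test is stated.** Aim 4 is to examine acceptability. The SAP confines itself to Aims 1 to 3 and leaves Aim 4 to qualitative methods, applied in each setting and specified elsewhere. That plan may never contrast the ratings.

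The last point cuts both ways. An evaluation within each setting gets no benefit from cancellation, and these documents contain no plan for the ratings that would deal with the problem. What stands is a risk of inflated levels, and a reason for care in any comparison.

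**Conclusion.** The concern holds in a limited form. Facilitators administer and collect ratings of sessions they led, in small groups, with no shielding described. Courtesy bias may inflate those ratings in both MB arms, and possibly more in the HV-led arm. Whether there is a differential, and its direction and size, cannot be determined from the protocol or SAP.

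The reach is the checklist component of Aim 4 only: at most 4,698 forms, on the assumptions of 29 implementing sites, 27 women per site and full attendance. The interviews, the QIDS-SR16 and Aims 1 to 3 are untouched. The point is worth acting on because the remedy costs almost nothing, not because a bias of known size has been shown.

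**What to change.** Amend both places in Protocol section 4.0 (Program Intervention and Acceptability). Each woman places her completed form, labelled with study ID only, in an envelope and seals it. The envelope goes unopened to the research team. The form states that facilitators will not see the answers. The facilitator would still be in the room, but the answers would no longer be visible to her.

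The cost is envelopes, some handling, and the loss of immediate feedback to facilitators. Sending the three questions by REDCap link after the session is a fallback only: it exchanges possible courtesy bias for non-response, and section 4.0 acknowledges that some women lack internet access.

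The separate Aim 4 plan should say how the ratings will be summarised and whether they will be compared by arm. The SAP reports site implementation in the past tense, so many forms may already exist. For those, report the collection method as a limitation, read the ratings against the independently conducted interviews, and do not treat similar checklist scores alone as evidence of equal acceptability.

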8.0 Consent Process

All recruitment and consent procedures will be performed in accordance with guidelines of the Northwestern University Institutional Review Board. Women enrolling in the 42 home visiting programs during recruitment periods will complete the screening administered by phone by the Research or Intervention Coordinator. We request a waiver of written documentation of consent in order to administer this study online, or over the telephone if client participants do not have easy access to web-based resources. Online study implementation will decrease the time required to complete study assessments, and is more feasible to implement given that home visiting programs and clients across the State of Illinois and adjacent states will be participating, and our resources are limited.

Regardless of whether or not the study participant consents to the study online or over the phone, NU Research staff will offer the participant a copy of the consent form. If the study participant would like a copy of the consent, Research staff will either email or mail a copy of the consent form to the participant per their preferred method of contact.

If the enrollee meets eligibility criteria and is interested in participating in the study, the Research or Intervention Coordinator will indicate that a web-link with instruction on completing the baseline assessment via REDCap will be emailed or texted to them within the next two weeks. Consent will

be conducted using online administration at the time of the first web-based survey. A preamble to the consent form will appear in REDCap on the screen prior to the participant reviewing the consent. This preamble will be an introduction to the consent form clearly explaining the participant's role as a research participant in the study. The preamble will read: "The purpose of this study is to learn how well the Mothers and Babies program* works to help pregnant women and new mothers manage stress and reduce depression, when delivered by different types of facilitators. We are asking you to take part in this research study because you are receiving services from a home visiting program or an early childhood program and you are in your 2nd or 3rd trimester of pregnancy. Your participation in this study will last approximately 6-12 months after you complete your first survey. You will be asked to complete surveys that ask about your mood, stress, social supports, and involvement in prenatal services. Surveys will take approximately 45 minutes to complete, and will be conducted at the beginning of the study, immediately following completion of the 6-week group sessions, 3-months after the birth of your child, and 6-months after the birth of your child. You can complete these surveys on the internet or by phone. You may also be asked to participate in a brief interview about your experience with the Mothers and Babies program. The interview will be conducted over the phone and will last approximately 30-60 minutes."

*The Mothers and Babies program intervention is described fully to the participant during the screening process prior to consenting into the research study. The preamble will be available in both English and Spanish.

A brief questionnaire will follow the consent form in order to ensure the participant understands that (1) their participation is voluntary, and (2) they may withdraw or refuse participation at any time without consequence to their home visiting services. Both the online consent form and the study surveys for home visiting clients will be available in English and Spanish. Each time a study participant fills out a survey, the survey will include a prompt to the participant asking if they wish to continue their participation by completing the next survey.

We are requesting a waiver of parent permission in order to waive the signature of parents of children who are participants (Pregnant women >16years old; < 18 years old). This research involves minimal risk to the participants by only requiring the administration of online surveys and/or telephone interviews in order to collect data. Guidance from the U.S. Department of Health and Human Services Office of Research Protections (OHRP) indicates that individuals < 18 years of age can consent to study participation without parental consent if the study procedures for which they are consenting are such that they could provide consent outside of the research context. The waiver of parent permission will not adversely affect the rights and welfare of the minor subjects. This is a low-risk study. We will assess the Minor's ability to consent to participate by asking them a series of questions at the end of the informed consent process to ensure they understand 1) the main points of the study, including the research requirements, 2) the main risks of the study (in our case, feeling uncomfortable about some of the mental health questions, and 3) understanding that they can refuse to answer any questions on assessments and/or opt out of the study at any time w/o adversely affecting their relationship with their HV program.

This research could not practically be carried out without the waiver of parent permission. Home-Visiting Program protocol is that parent/guardian consent is not required for a client under 18 to be able to enroll in a home-visiting program. The minors who we anticipate enrolling into the study have fractured relationships with their parents given the predominately low-income populations we are working with. This will result in difficulties tracking down the parent/guardian for informed consent.

The Intervention Coordinator and RA are bilingual and, therefore, able to communicate with both

English- and Spanish-speaking participants. All of the surveys and assessments provided to the participants will be in either English or Spanish and administered either orally or written in the language in which the participants are most comfortable speaking.

The Research/Intervention Coordinators and the RA will conduct the semi-structured interviews. All home visitors and mental health professionals will be asked to provide informed consent prior to participating in their semi-structured interview. Consent forms will clearly indicate that some study participants will be asked to participate in this additional data collection activity.

For the home visiting supervisors/managers/directors who are interested in participating in the survey, the Research Coordinator will email the web-link with instruction on completing the survey via REDCap within one week of interest in completing the survey. Consent will be conducted using online administration at the time of the survey.

9.0 Process to Document Consent:

We request a waiver of written documentation of consent in order to administer this study online, or over the telephone. Online consenting will take place in Northwestern University's secure REDCap Database. There will be a continuous prompt to participants when filling out surveys regarding their current willingness to continue participation.

Instructions to the REDCap assessments will provide rationale for the use of certain survey questions. Research team members administering assessments via phone or in person will be instructed to make sure this rationale is provided to study participants who do not see this rationale on the web-based REDCap system. Participants will be informed via informed consent and during all assessments that they may choose to not answer any question at any time for any reason and that not answering questions will not affect their relationship with their HV programs or ability to keep receiving the MB intervention (for those enrolled in the two intervention arms). Research assistants will consult with the Research Coordinator and PI, [name], if necessary, to resolve any questions they are unsure how to handle.

10.0 Risks to Participants:

There are no major risks to study participation. A participant in the study may experience some psychological discomfort while answering questions that may be considered of a sensitive nature about herself, her child, or her family. Study participants randomized to the MB intervention group may also experience some discomfort discussing stressful life events. Facilitators leading MB intervention groups will be specifically trained on protocols to handle such situations. Should a participant wish to withdraw from the study for any reason, at any time, her access to home visiting program services will not be affected. It is within reason to expect there may be participants who experience and endorse some level of suicidality during the study. Any study participant who expresses suicidal thoughts on assessment instruments (including baseline screening) or during intervention activities will be referred to the supervisor at the home visiting program. The supervisor, who is trained in responding to and addressing suicidal ideation, will use their agency's protocol to make a determination regarding whether the study participant is in danger of harming herself or others and will determine necessary steps to ensure the safety of the study participant. Other psychosocial concerns that may be raised among study participants during study intervention activities (i.e. substance abuse and domestic violence, will be closely monitored) per usual home visiting program protocols. Should home visitors become aware of these psychosocial risks, referrals will be made to an appropriate social service agency using protocols used by their home visiting program.

We do not anticipate any circumstances under which subjects will be withdrawn from the research without their consent. If a subject withdraws from the research, we will no longer collect survey data, but we will use data already collected unless the subject submits a written request to withdraw their data.

11.0 Potential Benefits to Participants:

There may be no direct and immediate benefits for individuals participating in the research component of this study. We believe that women randomized to the MB Course will exhibit greater reductions in depression symptoms, perceived stress and improved parenting.

12.0 Financial Compensation:

Participant outcomes will be collected at four time points—baseline, post-intervention, 12 weeks postpartum, and 24 weeks postpartum. Participants will receive \$20 remuneration at the baseline, 12-week and 24-week assessments. They will also receive \$20 if they are randomly selected for a qualitative interview post-intervention. The post-intervention assessment consists of one depressive symptom measure, so no remuneration will be provided.

Both the participants who complete the surveys online via the unique link sent to them by Research staff from the NU REDCap Database and those participants who decide to take the surveys verbally by phone, will receive their gift cards by mail once the survey has been completed.

There are no costs to participate in the study. We have budgeted for childcare and transportation for study participants requiring assistance in these areas. HV stakeholders involved in developing this project strongly supported the inclusion of transportation and childcare reimbursement.

13.0 Provisions to Protect the Privacy Interests of Participants:

We will use several procedures to secure data to maintain its confidentiality. Only authorized persons will be granted access to study data. Currently, this includes the PI ([name]), Project Manager ([name]) and Study Coordinators ([name] and [name]). Only authorized persons will be allowed to enter and view study data. Passwords and system ID's for the REDCAP system will not be shared with other team members. Additionally, the physical security of the workstations and files where REDCAP data are stored will be maintained by study personnel. All data collected will be de-identified using a study ID. The only document with identifying information is the consent form.

14.0 Confidentiality and Data Management:

Only the research team will have access to individually identifiable private information about human subjects, for the purpose of tracking recruitment and retention, as well as participation payments. All data will be de-identified in study databases.

To safeguard confidentiality and anonymity, all data collection instruments will identify participants only by study ID number. Logs linking information to study numbers will be kept locked in a file cabinet in the Project Manager's office. Data analysis staff will not have access to identifying information. We will inform participants of the areas to be covered in the surveys prior to their administration. Study participants will be told that if they experience any discomfort while participating in the data collection procedures they can ask to be removed from the study. Also,

participants will be told that they do not have to respond to any questions that make them feel uncomfortable. Individuals will be told that their refusal to answer any question will not jeopardize their relationship with their home visiting program and will not affect their receipt of home visiting services.

We believe that the use of the REDCAP data collection system will allow us to collect high quality data from all study participants and will not require the need for additional procedures to monitor data quality.

Power Analysis: For our **superiority analyses** (Aim 1) comparing MB led by home visitors vs. usual care, we have assumed a standard deviation of ~6.0 points on the QIDS-16—our measure of depressive symptoms. We anticipate over 95% power to detect a five-point difference between study arms (HV- led MB vs. usual care) with ICC's up to .01; thus, the planned sample size and anticipated dropout rate provide adequate power to detect meaningful differences across arms for our superiority analysis. We have also conducted power and sample size calculations that take into consideration the possible loss of clusters (i.e., HV programs) within each study arm. Even with a loss of two clusters implementing MB and one cluster providing usual care, we will have over 90% power to detect a five-point difference between study arms on the QIDS-16. Previous published prevalence data and previous MB data illustrate a 15% reduction in incidence of depressive episodes, and again, we anticipate minimal ICC. We expect power >95% to detect an absolute risk reduction of 15% in the intervention arm for ICCs no larger than 0.01.

For our **non-inferiority (NI) analyses** (Aim 2) comparing MB led by home visitors vs. MB led by mental health clinicians, we used similar assumptions of a 6.0 SD on the QIDS-16. We will have >85% power to detect a difference in mean QIDS-16 scores of two points between the two arms with 1224 analyzable participants' data (i.e., 612 in each arm, or 18 clusters in each group with 34 participants on average) with an ICC no larger than .01. We have taken into consideration the potential loss of up to two clusters in each study arm for our NI analyses. Even with a loss of two clusters, which would leave us with 1064 analyzable participants' data (i.e., 532 in each arm), we will have >80% power to detect a difference in mean QIDS-16 scores of two points between study arms with an ICC no larger than .01. Since we recognize that power to claim NI will depend heavily on the magnitude of any ICC, we will perform several ICC calculations within each arm to assess power assumptions post hoc. We do not anticipate adequate power to claim NI regarding the incidence of new cases of major depression. If we assume 15% incidence in the professional arm versus 20% in the paraprofessional arm (i.e., a margin of NI of 5%), a sample size of 1224 participants would have 64% power and a sample size of 1064 would have >50% power at the 5% level of significance without accounting for any ICC. Thus, we will statistically compare the two arms with respect to MDD incidence, but do not anticipate the ability to claim NI.

15.0 Data Monitoring Plan to Ensure the Safety of Participants:

Any study participant who endorses thoughts of self-harm will be referred to the supervisor at the home visiting program, by the study coordinator. The supervisor, who is trained in responding to and addressing suicidal ideation, will use their agency's protocol to make a determination regarding whether the study participant is in danger of harming herself or others and will determine necessary steps to ensure the safety of the study participant. The Principal Investigator will be notified

immediately of any such referrals made by study staff. In addition, should administration of depression scale indicate the participant is experiencing severe depressive symptoms, the supervisor at the home visiting program will be notified in order to provide appropriate referrals for their client's mental health treatment linkage.

We will administer the Maternal Mood Screener (MMS) (Le & Muñoz, 1998) to assess for history of MDD and current MDD. The MMS is a self-report checklist that assesses MDD using DSM-V criteria. Previous research supports the MMS as a valid instrument for MDD screening (Vasquez et al., 2008). Women meeting MDD criteria who are not currently in treatment will be referred to the supervisor at their HV agency.

During any of the research assessments, if the participant endorses current thoughts of harming herself or others, the following protocol should be followed, and documented on an Incident Report.

Maternal Mood Screener (MMS), Question 9d

→ *In the past 2 weeks, subject endorses she has attempted suicide in the past two weeks*

The Quick Inventory of Depressive Symptomatology (QIDS), Question 12

→ *In the past week, subject selects answer #3 (I thought of suicide or death several times a day in some detail, or I made specific plans for suicide or actually tried to take my life)*

The Edinburgh Postnatal Depression Scale (EPDS), Question 10

→ *In the past week, subject endorses thoughts of harming herself quite often*

When assessments are completed over the phone or online during regular business hours the following protocol will be completed within 24 hours.

Within 24 hours of the study participant's completion of their assessments a member of the Research team will call the study participant and will let the participant know that he/she will be contacting their home visiting program to let them know about the difficulties they are having with thoughts about death/suicide/hurting yourself/others, so they can reach out and offer support. The research team member will ask the study participant the following questions:

- "Are you thinking about killing yourself?"
- "Have you ever tried to hurt yourself before?"
- "Have you thought of ways that you might hurt yourself?"
- "Do you have pills/weapons in the house?"
- "Do you think you might try to hurt yourself today?"
 - If her response is Yes, then call 911 and stay on the phone with her until help arrives

All individuals that complete the above surveys will receive the following resources immediately upon answering the above answer choices on the noted assessments

- ✓ Home Visiting Program Office phone number
- ✓ National Suicide Prevention Hotline (24/7)
 - [name] ([name])
 - <http://www.suicidepreventionlifeline.org/> (online chat available 24/7: "Lifeline Chat")
- ✓ Postpartum Support International (outside of Illinois)
 - [name]
- ✓ NorthShore Perinatal Support, 24-hour Crisis Hotline (in Illinois)
 - [name] [contact])

All of these resources (except the home visiting program office number) will also be shared with all study participants, regardless of answers to assessment questions, at the end of each assessment.

The research team member will stay on the phone with those individuals who endorse the possibility of imminent self-harm. After the research team member ends the call with the study participant, they will call the Program Manager with relevant details, reporting what the client said and endorsed, as well as the information they gathered during the assessment and call with the participant. The research team member will then follow up with an email to the home visitor, supervisor, Project Manager, as well as the PI with relevant details.

If the survey is completed outside of regular business hours (i.e. weekends/holidays) the research team will follow-up with the participant no later than the following business day. As noted above, the risk would be acknowledged in real time as the participant would still receive resources immediately following their answer selection to the above survey questions.

We believe this to be a reasonable expectation in regards to protecting human subjects and the role of the research team. Previous Mothers and Babies studies conducted by the PI, as well as other nationally representative studies of perinatal women have shown that less than 1% of study participants will endorse the most “severe” response choice on survey items related to suicidality. As such, we anticipate that the number of study participants who endorse the most severe response related to suicidality outside of regular business hours over the course of this study will likely be < 10 individuals. As such, we believe our approach to handling this potential risk to study participants—i.e., immediate provision of 24/7 resources and follow-up by the study team no later than the next business day—is reasonable given its likelihood of occurrence. Moreover, women receiving the Mothers and Babies intervention (~86% of the sample) will be receiving information on modifying harmful thought patterns that may contribute to decreased thoughts about self-harm.

16.0 Data and if applicable, Specimen Banking:

